14. PROVISIONS TO MONITOR THE DATA TO ENSURE THE SAFETY OF SUBJECTS*

The device is not intended to induce any shock to participants. There is an extremely low chance that participants may experience electrical shock as a result of having sensors directly applied to participants' skin. This is similar to experiencing static shock from rubbing against the carpet. However, if they do, the severity is also extremely low. In order to minimize subject harm as a result of being shocked by the sensors, room temperature will remain above 65 degrees when running participants as the colder, drier air is more likely to cause static shock. We will also follow all safety guidelines for the equipment. These include having participants wash their hands thoroughly, then use hand sanitizer, and then use an alcohol towelette to clean the finger the sensor will be placed. In addition, participants will be instructed to try to keep their hand still during the study to ensure the sensor does not move.

15. WITHDRAWAL OF SUBJECTS WITHOUT THEIR CONSENT*

NA

16. RISKS TO SUBJECTS*

Risks to subjects involve experiencing a minor static shock as explained in #14 as well as being uncomfortable answering questions about tobacco use. Participants will be advised that they are free to refuse to answer any question that makes them feel uncomfortable. All observed or volunteered adverse events will be recorded through the IRB. Lastly, participants will be at

INVESTIGATOR STUDY PLAN - REQUIRED

some risk of breach of confidentiality, which is the case with most research studies. There are no known or suspected risks to pregnant women who may coincidentally be enrolled.

17. POTENTIAL DIRECT BENEFITS TO SUBJECTS*

NA

18. VULNERABLE POPULATIONS*

- **Students or employees:** Students or employees of the University of Massachusetts Medical School will be eligible to enroll. Contacts with the study participants will be for assessment purposes only. No one on the research team supervises or has the ability to influence a subject's grades, academic success, or professional advancement. The PI on this project does not teach courses at this time. Since many students may fall in the study population criteria, we are requesting to advertise the study on student list servs (The Student Life Bulletin, The Graduate School of Nursing list serv, and School of Medicine list serv). When participants come for a visit, they will not be asked if they are a UMass Chan student.
- **Adults unable to consent:** Our recruiting and consent process (requiring us to see the adult in person and have them sign the consent form) will allow us to identify adults who do not have the capacity to consent. They are ineligible to participate.
- **Subjects who are not yet adults (infants, children, teenagers):** Individuals under the age of 18 are ineligible to participate.
- **Pregnant women:** Pregnant women may be included in this research study. These requirements will be followed: No inducements, monetary or otherwise, will be offered to terminate a pregnancy. Individuals engaged in the research will have no part in any decisions as to the timing, method, or procedures used to terminate a pregnancy. Individuals engaged in the research will have no part in determining the viability of a neonate.
- **Neonates of uncertain viability or non-viable neonates:** NA
- **Prisoners:** We will not enroll or conduct research procedures with individuals that are known to be prisoners. If enrolled subjects become incarcerated during the study, we will submit this information within five business days as Reportable New Information.

19. MULTI-SITE RESEARCH*

NA

20. COMMUNITY-BASED PARTICIPATORY RESEARCH*

NA

21. SHARING OF RESEARCH RESULTS WITH SUBJECTS*

It may be several years before the results of the research are available. If participants are interested in the results of the study, the research team will request participants' contact information to reach them when results are available. We can share participants' individual results with them if they ask. However, because these are research tests, they are for their interest only. The results cannot tell participants about their health or diagnose any condition. If they request the information, the results can be provided at the conclusion of the study via email.

INVESTIGATOR STUDY PLAN - REQUIRED

22. SETTING

The study will take place at the Prevention Institute at the Shaw Building (5 minute walk from Sherman Building where office is located). The lab is a facility for conducting focus groups, interviews, and message communication material testing. The lab provides Internet access on Mac and PC computers to collect the survey responses. The lab also contains iMotions software and hardware which enables the collection of psychophysiological data using sensors. The data entry and analysis will take place at the Shaw and Albert Sherman buildings. In the event that data analysis takes place remotely (e.g., the research team's home), the members will use UMass Chan computer with UMass Chan secured network.

23. RESOURCES AVAILABLE

The PI is responsible and accountable for the implementation of the study in accordance with the proposed plan. The PI holds a doctoral degree and has extensive research experience including the conduct of a variety of studies relevant to the current study.

The Study Coordinator is a postdoctoral research fellow who holds a doctoral degree and has experience in research studies. The coordinator will coordinate and execute day-to-day activities at the study site and implementation-related tasks (recruitment and retention, running participants, survey assessments, laboratories, and data management, participant compensation). The postdoctoral fellow is responsible for obtaining the informed consent from participants. The postdoctoral fellow will devote 50% of their time to ensure the launch and completion of this study, as well as data cleaning, analysis, and dissemination.

The PI and/or postdoctoral fellow will meet with any staff member involved with this research via Zoom and in person to ensure that they are fully informed about the protocol and the research procedures. Furthermore, the PI and/or postdoctoral fellow will meet with the staff members at least once a week to review their specific duties and functions (e.g., setting up study, data analysis).

24. LOCAL RECRUITMENT METHODS

We will recruit 112 young adults between the ages of 18 and 24. Participants will be recruited from the greater Worcester area using email (See Appendix-C), flyers, and social media, advertising an opportunity to participate in a health messaging study. We will also send out the flyer to the following student list servs at UMass Chan: The Student Life Bulletin, The Graduate School of Nursing list serv, and School of Medicine list serv. Participants from other studies will also be contacted. Passive online screener will be used to determine eligibility. Potential participants will be directed to an online screener that will collect their contact information. Those who meet the eligibility criteria will be contacted to schedule the first visit.

\$60 will be given to each participant at the conclusion of their visit in the form of a gift card. We will follow the policy of participant payment instruction. The gift cards will be given out per the req of partici payment through email and text message. We will collect participants' email addresses and any other info required by participant addresses to send them their gift card at the end of their visit. The gift cards will be sent from a umassmed.edu account within an hour after their visit. Then, the record of the participant's email address and address will be destroyed by the PI.

INVESTIGATOR STUDY PLAN - REQUIRED

While this study is requesting to advertise to UMass Chan students, we do not aim for them to be the only participants in the study.

Additionally, participants will be recontacted if they meet the eligibility criteria to ask if they would be willing to be contacted to participate in future studies. Depending on their preferred contact method (e.g., email or phone), participants will be contacted via that method and asked if they would be willing to be contacted for future studies. There will be three attempts to contact participants. We will keep a list of those who say “no” (which include those who do not answer after the three attempts) and those who say “yes.”

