1. TITLE

Identifying and examining the effects of source and presentation on responses to electronic cigarette public education messages in young adult vapers and non-vapers – Part 2

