The proposed research is guided by biobehavioral theories of tobacco regulatory science,^{39,40} psychology,^{15,41} and communication.^{42,43} By using previously tested education messages,⁴⁴ we will determine an optimal combination of message source and presentation type to increase message acceptance and e-cigarette harm perceptions. We will compare the effects of two sources (expert and peer) and two message presentation types (one-sided and two-sided) for young adult vapers and non-vapers. We will use in-lab study for objective assessment of psychophysiological measures (heart rate, skin conductance, and eye-tracking) during message exposure (N=112) to determine optimal messaging. The goal of this study is to determine optimal message source and presentation for young adult vapers and non-vapers to increase message acceptance and harm perceptions using psychophysiology.

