6. INCLUSION AND EXCLUSION CRITERIA*

INVESTIGATOR STUDY PLAN - REQUIRED

We will recruit young adults (N=112; 18-24 years) from the greater Worcester area, who identify as 1-a) vapers (n=56) or 1-b) susceptible non-vapers (n=56) and fluent in English. All participants will have confirmed 12+ hour abstinence from ingesting tobacco/cannabis prior to beginning the study in the lab

Those who are not fluent in English will not be included in the study. Prisoners will not be included in the study. Pregnant women may be in the study if they choose, but we will not seek pregnant people to be in the study.

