11. PROCEDURES INVOLVED*

After providing informed consent, participants will be randomized to one of four experimental conditions in a 2 (Source: expert and peer) x 2 (Presentation: one-sided and two-sided) design. Data will be collected through iMotions, a psychophysiological data collection platform. We will track participants' eye movements using an eye-tracking device. We will assess heart rate and skin conductance with a sensor by attaching Velcro-strapped electrodes on the fingers of participant's nondominant hand. When the study begins, participants will complete pretest measures, view messages, during which they will be measured on their psychophysiological responses, and complete posttest measures. Messages (see Appendix-A) will be presented in a random order for at least 10 seconds. Between each message segment, a black screen and "get ready" screen will be presented for 10 seconds to return participants' heartrate and skin conductance levels to baseline. This meets the established amount of time (6 seconds) to collect heart rate and skin conductance.⁴⁵ This procedure will be repeated 18 times for the 18 messages. Finally, participants will complete measures on demographics, attitudes, and behavioral intentions. The entire procedure will take approximately 45 minutes. After completion, participants will be thanked and compensated \$50 for participation. Participants will be extensively debriefed about the hypothetical nature of the message source, the health harms of using any tobacco product, and information about the Massachusetts Tobacco Quitline with contact information. We will provide a consent form and verbally reiterate this information.

In order to minimize subject harm as a result of being shocked by static electricity from the sensors, room temperature will remain above 65 degrees when running participants as the colder,

INVESTIGATOR STUDY PLAN - REQUIRED

drier air is more likely to cause static shock. We will also follow all safety guidelines for the equipment. These include having participants wash their hands thoroughly, then use hand sanitizer, and then use an alcohol towelette to clean the finger the sensor will be placed. In addition, participants will be instructed to try to keep their hand still during the study to ensure the sensor does not move.

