Cover Page for ClinicalTrials.gov

Document:

Statistical Analysis Plan

Official Study Title:

Responses to Message Source and Presentation Using Psychophysiology

Document Date:

January 17, 2024

Psychophysiological Testing

Study Design and Power Analysis:

We will assess which communication principles influence psychophysiological responses on visual attention, orienting response, and arousal to determine the features that can increase acceptance of e-cigarette education messages in young adults. Eligible participants will be randomly assigned to one of four experimental conditions in a 2 (Source: expert and peer) x 2 (Presentation: one-sided and two-sided) design. For the psychophysiological part of the Aim 1, we will recruit total 112 young adults (age 18 to 24) vapers and susceptible non-vapers. We will use stratified sampling, with n=56 for each vaping status. The estimation was based on Stevens et al.'s (2021) study. Based on simulations as in crowdsourcing study, participants per message condition gave stable ranks for the top 3 messages. We use a conservative approach and propose 7 participants per the message condition for each vaping status. I will use a multi-attribute decision-making (MADM) framework to produce a dataset containing data on participant response to each message with source + presentation type. I will merge crowdsourced and psychophysiological data to rank messages and determine optimal content. This technique has been used in our previous work. MADM provides a practical, transparent framework for considering data across multiple inputs, determining the relative importance of each attribute, and simultaneously evaluating detail at the attribute level and in a summary measure across all attributes using aggregate data.

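### Recruitment from other, unnamed studies is open and no listed criterion excludes people who have already seen these messages, which could dilute the source contrast and leave the lab and crowdsourced inputs to the ranking non-independent

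*Protocol*

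**What the plan says.** **Recruitment.** Besides email, flyers, social media and student lists, Protocol section 24 adds: "Participants from other studies will also be contacted". The other studies are not identified. On deciding who qualifies, the same section says: "Passive online screener will be used to determine eligibility". The screener's items are not in the public text.

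**Eligibility.** Section 6 admits 18-24-year-olds "who identify as 1-a) vapers (n=56) or 1-b) susceptible non-vapers (n=56) and fluent in English", with at least 12 hours of confirmed abstinence from tobacco and cannabis. It excludes prisoners and also states: "Those who are not fluent in English will not be included in the study". Section 18 rules out minors and adults unable to consent. Neither section mentions earlier participation or earlier sight of the messages.

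**Links to earlier work.** The title (section 1) ends "responses to electronic cigarette public education messages in young adult vapers and non-vapers – Part 2". Section 5 introduces the stimuli with "By using previously tested education messages". The SAP refers to a crowdsourcing study and says: "I will merge crowdsourced and psychophysiological data to rank messages and determine optimal content".

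**Debriefing.** Section 11 says of this study: "Participants will be extensively debriefed about the hypothetical nature of the message source".

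**The concern.** A ranking that merges two data sets needs messages common to both, so Part 1 very probably showed substantially the same messages. A person recontacted from Part 1 would then meet every listed criterion here.

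Three things are at stake.

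- **First-exposure responses.** The lab outcomes are heart-rate deceleration, skin conductance and dwell time, read as attention, orienting and arousal. A second viewing plausibly yields a different response from a first.
- **The source manipulation.** Source is only an instruction to imagine who wrote the message (Appendix A), and this study tells participants afterwards that the source was hypothetical. If Part 1 did the same, a returning participant already knows this.
- **The merge.** Someone present in both data sets links two inputs that the ranking would otherwise take as separate evidence.

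The documents describe no way to find such people later. There is no de-duplication step, exposure covariate or sensitivity analysis. Section 26 keeps responses under a numeric identifier that is not directly linked to identity and de-identifies them when enrolment closes. Section 24 has the payment contact record destroyed. Screening is therefore the practical point of control.

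**Working it through.** **Step 1: the plan's sample size.** The SAP gives 112 in total, 56 per vaping status and 7 per message condition per status.

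- Four conditions: 7 x 4 x 2 = 56, which does not match.
- Eight cells (the four source directions in Appendix A x two presentations): 7 x 8 x 2 = 112, which matches.

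The eight-cell reading is inferred from Appendix A. With the four stated conditions, each cell holds 56/4 = 14 per vaping status. Cells are therefore 7 or 14, depending on the reading. The SAP should say which is meant.

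**Step 2: dilution.** Let f be the share previously exposed and r the fraction of the condition effect lost in those people. Then

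observed effect / true effect = 1 - f x r.

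The documents give neither f nor r, so all values below are assumptions. The SAP states no alpha, power or effect size, so the power figures are only a yardstick. They take a source contrast within one vaping stratum, 28 v 28, two-sided 0.05, with 80% power before dilution. The effect so detectable is d = (1.96 + 0.84) x sqrt(2/28) = 0.75. Diluted power is Phi((1 - f x r) x 2.80 - 1.96).

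| f | r | Effect retained | Power |
|---|---|---|---|
| 5% | 25% | 98.75% | 79.0% |
| 10% | 50% | 95% | 75.9% |
| 25% | 50% | 87.5% | 68.8% |

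The first row is negligible and the third is not.

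**Step 3: exposure within a cell.** The chance that a cell of 7 holds at least one exposed person is 1 - (1 - f)^7, which gives 30% at f = 5%, 52% at 10% and 87% at 25%. One such person is 1/7 = 14% of the cell.

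**Step 4: vapers versus non-vapers.** Vaping status is not randomised, so f may differ between strata. If 25% of vapers and 5% of non-vapers were exposed, with half the effect lost (all assumed), the retained effects would be 1 - 0.25 x 0.5 = 0.875 and 1 - 0.05 x 0.5 = 0.975. If the true effect were the same in both groups, they would still appear to differ by a tenth of it.

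**Step 5: the merge.** Take two equally weighted data sets of equal size, a share f of people in both, and correlation rho between one person's two scores. The variance of the merged mean is (1 + f x rho) times its value under independence: 1.015 at f = 5%, rho = 0.3, and 1.35 at f = 50%, rho = 0.7 (all assumed). The expected mean, and so the expected order of messages, does not change through this route.

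**Step 6: effect of the remedy on N.** Screening exposed people out leaves the target at 112. Enrolling them and setting them aside later would need 112/(1 - f): 118 at 5%, 125 at 10% and 150 at 25%.

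**The case against.** A reader might infer that carry-over from Part 1 will blunt the responses, pull the arms together and let the same people count twice in the ranking. The documents do not support that much.

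- **Source of recruits.** Section 24 does not say that the other studies are the team's own or that Part 1 is among them. Part 1 is described only as crowdsourced, whereas this study recruits from greater Worcester for a lab visit. Overlap could be close to nil. This stands.
- **Same messages.** The merge strongly implies it, but it is not stated. Nor is any debriefing in Part 1.
- **The screener.** It may already ask about earlier participation. The gap is shown only for the listed criteria.
- **Direction.** No document gives a habituation or carry-over effect, and someone who earlier saw the other source could show a contrast effect instead. Randomisation balances prior exposure over the four conditions in expectation. It does not restore the contrast within exposed people, so dilution is the likely result but not an established one.
- **Sidedness.** Section 11 randomises people to one presentation and describes 18 messages. Section 26 has each participant go through both sidedness conditions, 36 messages in all. If section 26 holds, everyone sees both versions by design, and earlier sight of the other version is not distinctive. The sidedness argument must wait until these sections are reconciled.
- **Double counting.** The SAP's framework works on aggregate data and states no test or interval for the merged result. Overlap weakens independence without in itself moving a rank.

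These points limit the size of the problem. They do not supply the missing criterion.

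**Conclusion.** The point holds as a gap in eligibility. The plan invites participants from unspecified earlier studies, and nothing listed keeps out people who have seen these messages. If Part 1 participants enrol, the likely consequence is dilution of the source contrast, together with possible confounding of the non-randomised vaper versus non-vaper comparison on which H1 and H2 rest. The merged inputs would also be less independent than they appear.

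The size is unknown. The assumed cases run from a negligible loss of one power point to a loss of about eleven. They rest on assumed exposure shares and effect losses, and on the inference that Part 1 showed the same messages and is among the studies contacted. The change is worth making because it costs little and the documents provide no means of detecting the problem afterwards.

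**What to change.** 1. **Protocol section 6.** Add an exclusion for anyone who took part in Part 1 or in any earlier study that showed these messages. Apply it with one item in the existing online screener, and with contact-list checks where such records exist.
2. **Protocol section 24.** Name the other studies, or state that recontact is limited to studies that did not show these messages. Recontact from unrelated studies can continue.
3. **SAP.** State that lab participants are screened to be absent from the crowdsourced sample, by self-report where records cannot be linked.
4. **Related text.** Reconcile sections 11 and 26 on whether each participant sees one or both sidedness versions.

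N stays at 112. The cost is one screener item, a few lines of text and slightly fewer recontact candidates. Self-report will miss people who do not remember or do not say, and list checks depend on records that the documents do not confirm exist.

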25. LOCAL NUMBER OF SUBJECTS

112 individuals will participate in the study.

26. CONFIDENTIALITY

Screener data will be stored on REDCap. REDCap is a secure web-based application for building and managing online surveys and databases. This application was developed at Vanderbilt University. If participants consent, we will retain the identifying information (name, phone number, email) from the screener data for 3 years after completion of the study to recontact subjects for future studies. However, the responses will be de-identified at the conclusion of the participant enrollment period. Thus, participants’ contact information will not be linked to the participant response. If participants do not consent to storing their contact information, we will destroy their contact information from the database at the conclusion of the enrollment period.

UMass Chan deploys REDCap application for use by our researchers and their study collaborators. Clinical study groups utilize REDCap functions via an intuitive interface to generate custom databases and/or surveys for data collection and study management including site and personnel management. REDCap provides audit trails for tracking data manipulation and export procedures, as well as seamless data downloads to common statistical packages and data import from non-REDCap data sources. UMass Chan REDCap is supported by the Data Sciences & Technology Division of Information Technology (IT).

The UMass Chan REDCap application resides in a secure network environment based on ISO 27002 designed to support PHI data capture and storage.

All study data are collected using the iMotions 6.4 Biometric Research Platform, a secure, computer-based data collection platform. No self-report or psychophysiological data collected are directly linked to participant identifying information: self-report and psychophysiological data collected through iMotions are tracked using a unique, numeric study identifier that does not contain any personally identifying information. A monitor on the computer will track the participant’s eye movements and three sensors on the participant’s fingers will track heart rate and skin conductance. Each message will appear for ten seconds, which falls above the established amount of time needed (6 seconds) to collect heart rate and skin conductance levels for still messages. This will allow us to take into account baseline levels and time for heart rate and skin conductance to react. After each message, participants will answer the same measures included in the participant survey pertaining to responses toward the message and source, and

INVESTIGATOR STUDY PLAN - REQUIRED

perceived message effectiveness. This process will be repeated 18 times for each of the two message sidedness conditions, resulting in a total of 36 different messages seen by participants. Afterwards, participants will be asked to complete additional measures related to actual message effectiveness (e-cigarette attitudes, risk beliefs, intentions to vape).

Between each message sidedness condition, individuals will see a blank black screen for 10 seconds, then a black screen with the words “get ready” for five seconds followed by another black screen for 10 seconds to return heart rate and skin conductance back to baseline. All methods are consistent with accepted standards of psychophysiological measurement for media studies.

[name] and the research team will be responsible for file maintenance. Screeners will be electronically maintained throughout the course of the study for scheduling participants. Signed consent forms will be stored in a locked cabinet through the course of the study and only retrieved for IRB requests. Participant surveys and psychophysiological data will be stored on a password protected storage on a secured network. Files will be reviewed once per week to ensure all documentation is securely stored. The researcher will first make sure the consent form is in the locked cabinet and then ensure that each participant file from iMotions is electronically stored for each participant ID number. Study documents will be maintained for a period of 3 years after completion of the study.

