10. STUDY ENDPOINTS*

The primary outcome measures include psychophysiological responses (cognition, arousal, attention) and self-reported measures of e-cigarette harm message and source perceptions (message acceptance, harm perceptions, reactance, message liking, source trust, attitudes, behavioral intentions).

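### Protocol section 11 and the SAP randomise sidedness between participants, but section 26 shows participants both versions, which would leave attitudes and intentions with no sidedness comparison.

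*Protocol*

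**What the plan says.** Protocol section 11 (Procedures Involved) states that "participants will be randomized to one of four experimental conditions", formed by crossing source (expert, peer) with presentation (one-sided, two-sided). On exposure it says: "This procedure will be repeated 18 times for the 18 messages". The SAP agrees on the randomisation: "Eligible participants will be randomly assigned to one of four experimental conditions", in the same 2 x 2 layout. It recruits 56 participants per vaping status and says the investigators "propose 7 participants per the message condition for each vaping status". It gives no count of messages per participant.

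Protocol section 26 (Confidentiality) describes the same session differently. The cycle of exposure and rating is "repeated 18 times for each of the two message sidedness conditions, resulting in a total of 36 different messages seen by participants". The next paragraph describes a sequence of black and get-ready screens that individuals see between the sidedness conditions.

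The primary measures in Protocol section 10 include "message liking, source trust, attitudes, behavioral intentions". Both accounts of the session place attitudes and intentions after all messages. Section 11 says: "Finally, participants will complete measures on demographics, attitudes, and behavioral intentions". Section 26 says: "Afterwards, participants will be asked to complete additional measures related to actual message effectiveness", and names attitudes, risk beliefs and intentions to vape.

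**The concern.** Someone assigned to a single presentation condition cannot also view both presentations. Under section 11 and the SAP, sidedness is a between-participant factor; under section 26 it is a within-participant factor. The two need different randomisation, give different amounts of data per ranked message, and call for different analyses (independent groups or paired data).

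Section 4 of the protocol makes self-reported response to sidedness an objective, and Aim 1 is to find the best source and presentation type. Under section 26 no participant has seen only one-sided or only two-sided messages when attitudes and intentions are taken. A pretest would not rescue the comparison, because a change score would reflect both exposures. The same loss would apply to harm perceptions if they are what section 26 calls risk beliefs and they are not also asked after each message; the text does not say.

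Heart rate, skin conductance, dwell time and per-message ratings could still be compared by sidedness under section 26. However, each Appendix A claim would be met twice, and a fixed block order would confound sidedness with order. Section 26 states no counterbalancing; the random message order in section 11 is given for the 18-message version only.

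**Working it through.** **Inputs.** 56 participants per vaping status and 7 per message condition (SAP); four conditions and 18 messages (section 11); 36 messages (section 26); four source directions and 18 one-sided/two-sided pairs (Appendix A). Assumptions: equal allocation within vaping status (no ratio is given), source stays between participants under section 26, and SD = 1 for a message score.

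**Step 1: the plan's own sample size.** Total = conditions x 7 x 2 vaping groups.
- Eight conditions (four Appendix A directions x two sidedness versions, one version per participant): 8 x 7 x 2 = 112, the stated total.
- Four conditions (the 2 x 2 as written, or four directions with sidedness within participants): 4 x 7 x 2 = 56, not 112.

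The stated total therefore fits between-participant sidedness. This is an inference, because the SAP does not define a message condition.

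**Step 2: can 36 be a total over different participants?** The wording of section 26 does not favour this. It counts 18 repetitions for each of two sidedness conditions, and it describes screens that individuals see between those conditions. Appendix A refers only to an assigned source condition, so it does not settle the matter.

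**Step 3: the two versions, per vaping status.**

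| Quantity | Section 11 / SAP | Section 26 |
|---|---|---|
| Messages per participant | 18 | 18 x 2 = 36 |
| Message exposures | 56 x 18 = 1,008 | 56 x 36 = 2,016 |
| Participants per source-by-sidedness version of a message | 56/4 = 14 | 56/2 = 28 |
| SE of that message mean, √(1/n) | √(1/14) = 0.267 SD | √(1/28) = 0.189 SD |
| Participants per version, four directions counted separately | 56/8 = 7 | 56/4 = 14 |
| SE of that message mean | √(1/7) = 0.378 SD | √(1/14) = 0.267 SD |
| One-sided-only v two-sided-only participants at the end-of-session measures | 28 v 28 | none |

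The ratio of standard errors is √2 = 1.41 in both pairs of rows.

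**Step 4: how the analysis would differ.** This is an illustration for a simple mean contrast that the documents do not plan. The standard error for sidedness within one vaping status is √(2/28) = 0.267 SD between participants. Within 56 participants it is √(2(1−ρ)/56), which is 0.158 SD for an assumed correlation of 0.3 and 0.104 SD for 0.7. This applies only to measures taken under both versions. For attitudes and intentions under section 26 there is no contrast to estimate. Varying the block order would let the end score compare orders, not sidedness.

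**The case against.** The strongest reply is that the design is not really in doubt. The two places that set it out, section 11 and the SAP, agree on the randomisation, and the outlier is a paragraph under Confidentiality. The screen sequence there resembles the reset that section 11 places between messages, so it may be that reset badly worded. This makes an editing error plausible. It does not remove the conflict: section 26 is a full account of exposure, rating and final measures, and someone building the session from it would run a different experiment.

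Second, the documents plan message ranking and multi-attribute decision-making, with no specified test of sidedness on attitudes or intentions. A score taken once at the end cannot be tied to a single message under either version. That is correct, but these are listed primary measures and sidedness is a stated objective. Section 11 leaves a group comparison possible; section 26 does not.

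Third, the numbers have limits, and these points stand. Equal allocation is assumed. For ranking, section 26 gives the smaller standard error, so that difference shows that the versions are not interchangeable, not that section 26 harms the ranking. The reading of eight conditions depends on an undefined term and on treating the four directions as separate assignments. The contradiction does not depend on it.

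The reset wording is a lesser matter. Section 26 does not exclude a reset between messages, but the text should be aligned because section 13 takes the second before viewing as the heart-rate baseline.

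**Conclusion.** The concern holds. The current text gives two incompatible designs for one of the two experimental factors, and nothing else in the documents resolves them. This conclusion rests on the wording alone.

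The loss for attitudes and intentions is conditional on section 26 being what is run. In that case the sidedness comparison goes from 28 v 28 per vaping status (56 v 56 overall, equal allocation assumed) to none. The participants behind each message mean double, from 14 to 28, or from 7 to 14 if the four source directions are counted separately. Measures taken after or during each message keep a sidedness comparison, but one that needs a paired analysis and control of block order, neither of which is specified. The passages must be reconciled, because the choice decides which primary measures can address presentation type.

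**What to change.** **Preferred.** Change section 26 to 18 messages in the participant's assigned sidedness only, with the section 11 reset between messages. This matches section 11 and the SAP and keeps a sidedness comparison for every primary measure. It costs protocol wording and a check that the iMotions script agrees, with no extra participants. The SAP should also define a message condition.

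**If 36 messages are what is run.** State in section 11 and the SAP that only source is between participants. Randomise sidedness block order within vaping status, and analyse sidedness as paired with a term for block order. Take attitudes, risk beliefs and intentions after the first block. This option has a price: those measures become a between-participant comparison of about 28 v 28 per vaping status without the within-participant precision, and a mid-session questionnaire may affect second-block responses. If the measures stay at the end, the SAP should say that they do not inform the choice of presentation type.

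If data have already been collected, the sponsor should state which version was run and analyse it accordingly.
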